## CLINICAL STUDY PROTOCOL SUMMARY

**Title of Study:** Validation of the Concept of COPD Control In Clinical Practice

**Protocol version:** 1.0

**Study Number:** REG-RES1503

**Chief Investigator:** [name]

**Clinical Research Organisation:** Respiratory Effectiveness Group

**Part study funder:** REG and Novartis

**Name of Active Ingredients:** NA

**Name of Investigational Product:** NA

**Phase of Clinical Development:** 4

**Number of Investigational Centres Planned:** approximately 10 Centres

**Country of the study:** International – Spain, France, UK, Ireland, Canada

**General Design and Methodology:**

This is a 21-month pragmatic non-interventional trial comprising one baseline assessment and 4 follow-up visits.

**Objectives:** The primary aims of the study will be to evaluate the:

- Levels of COPD control (vs poor COPD control) in an international cohort of routine care COPD patients, and
- The clinical implications of control status.

Secondary objectives of the study are to:

- Compare the utility of the COPD Control (as defined) as a tool to identify COPD impact and stability with the CAT and CCQ;
- Evaluate the role of “adequate” (i.e. guideline-recommended) treatment prescribing on COPD control.
- Identify demographic and clinical characteristics associated with COPD control
- Evaluate the cost-utility of patients with controlled (as compared to poorly controlled) COPD.

**Number of Patients Planned:** 328

**Study Population:** It is planned to enrol approximately 328 patients older than 40 years with a diagnosis of COPD. The diagnosis of COPD will be based on a post-bronchodilator FEV1/FVC<0.7 in patients smokers or smokers of at least 10 pack-years, in accordance with the Global Initiative for Obstructive Lung Disease (GOLD).

**Length of the Study:** Length of the study will be approximately 21 months from baseline screening to final patient follow-up.

**End of the Study:** Last patient’s last visit.

**Inclusion Criteria:** Patients may be included in the study if they meet all of the following criteria:

- Spirometry-defined COPD (i.e. post-bronchodilator FEV1/FVC<0.7)
- Age ≥40 years
- Smokers or ex-smokers of at least 10 pack-years
- In stable state (as judged by the investigator) at point of recruitment

**Exclusion Criteria:** Patients will be excluded from participating in this study if they meet any of the following criteria:

- Have any concomitant chronic respiratory condition other than asthma or bronchiectasis (e.g. cystic fibrosis, lung fibrosis)
- Have severe comorbidity with a life expectancy shorter than 2 years
- Are unable to understand the instructions of the study or to fill the questionnaires
- Are unwilling to sign the informed consent
- Are participating in another clinical study or clinical trial

**Investigational Product:** NA (non-interventional study)

**Placebo:** NA (non-interventional study)

**Clinical Study Protocol Study Number: REG-RES1503**

**Blinding:** NA (non-interventional study)

**Method of Randomisation:** NA (non-interventional study)

## LIST OF ABBREVIATIONS AND DEFINITIONS OF TERMS

### Table of abbreviations

Abbreviation	Definition
BMI	Body Mass Index
BODE	Composite COPD severity index: BMI, Obstruction, Dysnea, Exacerbations
CAT	COPD Assessment Test
CCQ	Clinical COPD Questionnaire
COPD	Chronic Obstructive Pulmonary Disease
CRF	Case report form
eCRF	electronic case report form
FEV1	Forced Expiratory Volume in 1 second
FVC	Forced Vital Capacity
ICS	inhaled corticosteroid
LABA	long-acting beta-agonist
SAB	Short-acting bronchodilator
SABA	short-acting beta-agonist
SAMA	short acting muscarinic antagonist
Mild to moderate disease severity	BODE/Ex $\leq 4$ points
mMRC	modified medical research council dyspnea scale
Severe / very Severe disease severity	BODE/Ex $\geq 5$ points

## Definitions

### Impact

Clinical impact refers to the current repercussion the disease has on the patient. According to the ECLIPSE study, patients with the same level of prognostic severity (FEV1 and/or BODE index) can have a wider distribution of across a range of clinical characteristics, such as dyspnea, HRQoL and 6-minute walking test (1). Within a given severity category of COPD, COPD is defined using a number of clinical variables: degree of dyspnea, the use of rescue medication, the limitations in daily physical activity and the usual sputum color, OR using validated questionnaires (the CAT and CCQ) (2, 3).

Table 1. Definition of COPD summary by COPD Severity Category

Impact	Mild to moderate severity (BODE/Ex ≤ 4 points)		Severe/very severe COPD (BODE/Ex > 5 points)	
	Low*	High	Low	High
Dyspnea (mMRC)	0 – 1	≥ 2	0 - 2	≥ 3
Rescue medication	≤ 3 times in the last week	> 3 times in the last week	≤ 2 times a day	> 2 times a day
Daily physical activity (time walked/day)	≥ 60 min	< 60 min	≥ 30 min	< 30 min
Sputum color ^	Absent or White	Dark	Absent or white	Dark
OR (if using validated COPD questionnaires to assess impact), either of the following:				
- CAT	≤ 10	>10	≤ 20	>20
- CCQ	≤ 1	>1	≤ 2	>2

### Stability

Clinical stability over time is defined as a composite of the following over a 3-month evaluation period:

1. Absence of exacerbation (including the inherent phase of recovery from the exacerbation), AND
2. Absence of significant clinical worsening\* during a period of time, that is, that stability includes the absence of significant clinical changes and/or the presence of improvement (positive changes).

\*The CAT and CCQ have demonstrated potential utility in evaluate clinical changes over time (4,5). Clinically significant deterioration has been described as being associated with a change of ≥2 CAT points (6) and/or a change of ≥0.4 CCQ points (6).

Table 2. Definition of COPD stability by COPD Severity Category

Clinical stability over time (3-month evaluation period)		Mild to moderate severity (BODE/Ex ≤ 4 points)		Severe/very severe COPD (BODE/Ex > 5 points)	
		Stable	Unstable	Stable	Unstable
No Exacerbations	Exacerbations	None	≥1	None	≥1
AND					
No Clinical Worsening	Changes in the CAT	<2	≥2	<2	≥2
	AND/OR				
	Changes in the CCQ	< 0.4	≥ 0.4	≤ 20	>20

## Definition of COPD Control

Control of COPD is defined as a composite of low disease impact, adapted to the patients' level of COPD severity, and clinical stability over time.

### *Mild to moderate disease severity (BODE/Ex $\leq 4$ points)*

**Controlled:** Patients are controlled if, at the time of evaluation, their COPD:

- Impact is low, i.e. all of the following criteria are satisfied:
  - Limited signs of dyspnea: mMRC 0–1
  - Minimal recent rescue medication (short-acting bronchodilator) usage:  $\leq 3$  times in the last week
  - Limited impact on daily physical activity:  $\geq 60$  minutes walked per day
  - Absence of sputum, or (if present) white sputum**OR**
  - CAT:  $\leq 10$ ,**AND**
  - CCQ:  $\leq 1$**AND**
- Clinically Stable in the last 3 months:
  - Absence of COPD exacerbations, AND
  - Any changes in CAT have been less than  $< 2$  points in magnitude, OR,
  - Any changes in CCQ  $< 0.4$

**Uncontrolled:** all others

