### *Severe / Very Severe Disease (BODE/Ex $\geq 5$ points)*

**Controlled:** Patients are controlled if, at the time of evaluation, their COPD:

- Impact is low, i.e. all of the following criteria are satisfied:
  - Limited signs of dyspnea: mMRC 0–2
  - Minimal recent rescue medication (short-acting bronchodilator) usage:  $\leq 2$  times a day
  - Limited impact on daily physical activity:  $\geq 60$  minutes walked per day
  - Absence of sputum, or (if present) white sputum**OR**
  - CAT  $\leq 20$**AND**
  - CCQ  $\leq 2$**AND**
- Clinically Stable in the last 3 months:
  - Absence of COPD exacerbations, AND
  - Any changes in CAT have been less than  $< 2$  points in magnitude, OR,
  - Any changes in CCQ  $< 0.4$

**Uncontrolled:** all others

Table 3. COPD Control definition represented in tabular form, by COPD severity

Patients with COPD will be defined as having controlled disease if they satisfy all of the following criteria		Mild to moderate severity (BODE/Ex $\leq$ 4 points)	Severe/very severe COPD (BODE/Ex $>$ 5 points)
IMPACT (cross-sectional evaluation)	Dyspnea (mMRC)	0 – 1	0 - 2
	Rescue medication	$\leq$ 3 times in the last week	$\leq$ 2 times a day
	Daily physical activity (time walked/day)	$\geq$ 60 min	$\geq$ 30 min
	Sputum color ^	Absent or White	Absent or white
	OR (if using validated COPD questionnaires to assess impact), either of the following:		
	CAT	$\leq$ 10	$\leq$ 20
	CCQ	$\leq$ 1	$\leq$ 2
AND			
CLINICAL STABILITY (longitudinal evaluation)	Exacerbations	None	None
	AND		
	Changes in the CAT	$<$ 2	$<$ 2
	AND		
Changes in the CCQ	$<$ 0.4	$<$ 0.4	

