longitudinal concept that requires the absence of exacerbations and deterioration in the aforementioned variables or in CAT or CCQ scores. Hence, control is defined as a condition that has both low impact (adjusted for severity) and stability (14).

Having proposed the concept of control in COPD, it is now important to establish whether it has clinical validity and utility, specifically in terms of predicting outcomes and guiding on-going COPD management (and/or whether the measure may benefit from further refinement).

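### The CAT and CCQ stability criteria in the control rule ignore the direction of change, contrary to the protocol's worsening-only definition, so some improving patients can be classed uncontrolled

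*Protocol*

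**What the plan says.** The Stability definition has two parts: no exacerbation, and no significant clinical worsening over three months. It then says that "stability includes the absence of significant clinical changes and/or the presence of improvement (positive changes"). It presents the thresholds as thresholds for getting worse: "Clinically significant deterioration has been described as being associated with a change of ≥2 CAT points", with 0.4 points as the CCQ counterpart. Section 1.1 takes the same line and calls stability a "longitudinal concept that requires the absence of exacerbations and deterioration in the aforementioned variables or in CAT or CCQ scores". Table 2 puts its CAT and CCQ rows under a label that refers to the absence of worsening.

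The rule under Definition of COPD Control is worded differently. For mild to moderate disease the CAT line reads "Any changes in CAT have been less than $< 2$ points in magnitude, OR", and the next line offers "Any changes in CCQ" below 0.4 as the alternative. The severe/very severe stratum repeats both lines. Anyone who fails the rule falls under "Uncontrolled: all others".

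The link between the two change criteria also varies. It is OR in the stratum text, AND/OR in Table 2 and AND in Table 3, which opens with "Patients with COPD will be defined as having controlled disease if they satisfy all of the following criteria". Neither table contains the magnitude wording, and neither puts a sign on the thresholds.

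**The concern.** On both questionnaires a lower score is better, so a fall is an improvement. A limit on the magnitude of change treats a fall of 2 CAT points like a rise of 2. The CAT line as written therefore fails patients whom the Stability definition counts as stable. The CCQ line has no sign and can be read the same way.

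Section 4.4.2 uses this rule at Visit 0 to form the controlled and uncontrolled groups. Section 4.3.1 compares those groups on the annualised rate of the composite endpoint, and the first primary aim in Section 2.2 is the level of control itself. If the text is coded literally, some improving patients are counted as uncontrolled. That lowers the measured level of control and changes who is in the comparator group. Choosing among the readings after outcomes are known would be a post hoc choice about the exposure definition.

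**Working it through.** The protocol states no figure for this point, so there is none to reproduce. The check applies each available reading to specific patients and then illustrates the spread under assumed distributions.

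**Inputs.** The thresholds are 2 CAT points and 0.4 CCQ points (Stability; Definition of COPD Control). The connectives are OR (stratum text), AND/OR (Table 2) and AND (Table 3). Δ is the change since the previous assessment; a negative value is an improvement. Every patient below has low impact and no exacerbation.

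**Readings.**
- S: ΔCAT < 2 and ΔCCQ < 0.4. Both signed, both required. It follows the Stability definition on direction and Table 3 on the connective.
- A: abs(ΔCAT) < 2 or abs(ΔCCQ) < 0.4. Stratum text, with CCQ also read as magnitude.
- B: abs(ΔCAT) < 2 or ΔCCQ < 0.4. Stratum text, with CCQ read as signed.
- C: abs(ΔCAT) < 2 and abs(ΔCCQ) < 0.4. Magnitude wording joined to Table 3's AND.

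| ΔCAT, ΔCCQ | S | A | B | C |
|---|---|---|---|---|
| −3, 0.0 | stable | stable | stable | unstable |
| −3, −0.2 | stable | stable | stable | unstable |
| −3, −0.5 | stable | **unstable** | stable | unstable |
| −3, +0.5 | unstable | unstable | unstable | unstable |
| +3, 0.0 | unstable | stable | stable | unstable |
| +3, +0.5 | unstable | unstable | unstable | unstable |

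The third row is the perverse case. Under A, a patient who has clearly improved on both scales is uncontrolled, while one who has improved on CAT alone is controlled.

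Under B, abs(ΔCAT) < 2 is false for every patient with ΔCAT ≤ −2, so the rule reduces to ΔCCQ < 0.4. Under S, ΔCAT < 2 is true for the same patients, so S also reduces to ΔCCQ < 0.4. B and S therefore agree on every CAT improver.

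Under C, every patient with ΔCAT ≤ −2 fails. This stays true if C's CCQ term is read as signed.

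The fifth row shows why the connective must be settled too. A CAT worsening of 3 points with CCQ unchanged is stable under either OR reading and unstable under S.

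**Illustration.** The protocol gives no distribution of change, so these values are assumptions: normal changes with mean 0, CAT SD 3 or 5 (rounded to whole points), CCQ SD 0.4 or 0.7 (rounded to 0.1) and correlation 0.3 or 0.7. The share improving by 2 or more CAT points is 31% (SD 3) or 38% (SD 5). Share of those improvers classed unstable:

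| CAT SD | CCQ SD | Correlation | S | A | B | C |
|---|---|---|---|---|---|---|
| 3 | 0.4 | 0.3 | 10% | 39% | 10% | 100% |
| 3 | 0.4 | 0.7 | 2% | 47% | 2% | 100% |
| 3 | 0.7 | 0.3 | 19% | 63% | 19% | 100% |
| 3 | 0.7 | 0.7 | 5% | 69% | 5% | 100% |
| 5 | 0.4 | 0.3 | 11% | 39% | 11% | 100% |
| 5 | 0.4 | 0.7 | 2% | 43% | 2% | 100% |
| 5 | 0.7 | 0.3 | 20% | 62% | 20% | 100% |
| 5 | 0.7 | 0.7 | 7% | 66% | 7% | 100% |

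Row by row, A minus S runs from 28 points (39 − 11) to 64 points (69 − 5). B minus S is zero throughout. If the sponsor kept OR with both criteria signed, no CAT improver would be unstable. The B column would then be the difference from that rule, and it consists only of patients whose CCQ worsened by 0.4 or more.

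**The case against.** A reader might infer that the rule requires a small CAT change, so that anyone improving by 2 or more points is automatically uncontrolled. The documents do not support this. The CAT line itself ends in OR, and passing the CCQ line is enough. The automatic loss needs Table 3's AND together with the magnitude wording of the stratum text, and no single statement of the rule contains both.

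It can also be argued that the intended direction is clear. The magnitude wording is attached to CAT only. The Stability definition, Section 1.1 and Table 2's row label all speak of worsening, and control is defined through stability. An analyst guided by those passages would read the CCQ change as signed, and reading B then does no harm to CAT improvers relative to S. It is also fair to say that a falling CAT is not proof of stability, because the definition excludes the recovery phase of an exacerbation.

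This limits the consequence but does not remove the conflict. The direction given elsewhere does not cancel explicit contrary wording in the rule that assigns patients, and that wording appears in both strata. The unsigned CCQ line leaves reading A open. The recovery-phase point does not apply to the patients in the working, who are exacerbation-free by construction.

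**Conclusion.** The point holds as an internal contradiction on direction, made worse by an unreconciled connective. The stratum text limits CAT change in either direction and leaves CCQ change unsigned, whereas the protocol's own definition lets only deterioration break stability. The effect on improving patients runs from none relative to S (reading B), through loss of those who improve on both scales (A), to loss of every CAT improver of 2 or more points (C).

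The percentages rest wholly on the assumed means, SDs and correlations. They apply to CAT improvers only and are not estimates of how far the level of control would fall. A stronger figure is tempting. With CAT SD 3 to 6, mean 0 and whole-point scores, the CAT line alone is met by Φ(1.5/SD) = 69% to 60% of patients if only worsening counts, and by 2Φ(1.5/SD) − 1 = 38% to 20% if magnitude counts. That comparison ignores the CCQ route, and it ignores patients who are uncontrolled anyway through high impact or an exacerbation. It should not be read as lost prevalence of control or as a measured dilution of the primary contrast.

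The sponsor should correct this before patients are classified, because the rule defines the groups being compared.

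**What to change.** In both strata of Definition of COPD Control and in Tables 2 and 3, state the change criteria as signed worsening, in line with the Stability definition: an increase in CAT of less than 2 points, an increase in CCQ of less than 0.4 points, and any decrease counted as stable.

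Choose one connective and state it in all of these places as an explicit decision. It determines how patients who worsen on one scale only are classed, so it should not be settled silently while the sign is being corrected.

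Use the same signed rule for group assignment at Visit 0 and for control status at Visits 1 to 3, and code it that way.

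The cost is an edit to two strata and two tables, plus the classification code. No new data are needed, since Tables 5 and 7 list CAT and CCQ at Visit −1 and at Visits 0 to 3.

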### *Severe / Very Severe Disease (BODE/Ex $\geq 5$ points)*

**Controlled:** Patients are controlled if, at the time of evaluation, their COPD:

- Impact is low, i.e. all of the following criteria are satisfied:
  - Limited signs of dyspnea: mMRC 0–2
  - Minimal recent rescue medication (short-acting bronchodilator) usage:  $\leq 2$  times a day
  - Limited impact on daily physical activity:  $\geq 60$  minutes walked per day
  - Absence of sputum, or (if present) white sputum**OR**
  - CAT  $\leq 20$**AND**
  - CCQ  $\leq 2$**AND**
- Clinically Stable in the last 3 months:
  - Absence of COPD exacerbations, AND
  - Any changes in CAT have been less than  $< 2$  points in magnitude, OR,
  - Any changes in CCQ  $< 0.4$

**Uncontrolled:** all others

Table 3. COPD Control definition represented in tabular form, by COPD severity

Patients with COPD will be defined as having controlled disease if they satisfy all of the following criteria		Mild to moderate severity (BODE/Ex $\leq$ 4 points)	Severe/very severe COPD (BODE/Ex $>$ 5 points)
IMPACT (cross-sectional evaluation)	Dyspnea (mMRC)	0 – 1	0 - 2
	Rescue medication	$\leq$ 3 times in the last week	$\leq$ 2 times a day
	Daily physical activity (time walked/day)	$\geq$ 60 min	$\geq$ 30 min
	Sputum color ^	Absent or White	Absent or white
	OR (if using validated COPD questionnaires to assess impact), either of the following:		
	CAT	$\leq$ 10	$\leq$ 20
	CCQ	$\leq$ 1	$\leq$ 2
AND			
CLINICAL STABILITY (longitudinal evaluation)	Exacerbations	None	None
	AND		
	Changes in the CAT	$<$ 2	$<$ 2
	AND		
Changes in the CCQ	$<$ 0.4	$<$ 0.4	

## 1. BACKGROUND

### 1.1. Introduction

Chronic obstructive pulmonary disease (COPD) is a broadly heterogeneous condition. Optimum therapeutic outcomes require treatment to be tailored to the different clinical characteristics and severity of each patient (7-9). To a certain extent, the Spanish Guidelines for COPD (GesEPOC) represent a model of transition towards personalized medicine (10). In these guidelines pharmacological treatment is established with a combination of two essential elements: (i) the determination of the clinical phenotype and (ii) evaluation of the level of severity with the use of a multidimensional index. Multiple therapeutic alternatives emerge from the interaction between these two axes (clinical phenotype and the level of severity), constituting the first step towards individualization of treatment, which has been followed by other national clinical guidelines (11).

However, this approach can overlook changes in the day-to-day activities or symptoms of the patient, changes that may warrant modifications to their existing treatment. Within each clinical phenotype and each level of severity of COPD there are patients with a range of different “expressions” (i.e. symptoms, activity limitations, short-term changes) of their disease. Thus, the concept of disease control may help to better assess the state of the patients and their likely response to treatment. A third axis (control of the disease) should help in therapeutic decision making and has been recently proposed (12,13).

The concept of control has been extensively developed in asthma but little-explored in COPD. Recently, however, Soler-Cataluña et al proposed a new definition/concept of control for COPD. The concept aims to help describe the current clinical “situation” of the patient and to provide a tool that will help guide optimum treatment approaches for patients with COPD(14).

The definition has two components: (i) COPD impact and (ii) COPD stability. “Impact” is a cross-sectional concept that evaluates the clinical status of a patient. It is static assessment corresponding to a specific moment and can be assessed by questionnaires (i.e. the COPD Assessment Test [CAT] or the Clinical COPD Questionnaire [CCQ]) or evaluated based on a patient’s degree of dyspnea, use of rescue medication, level of physical activity and sputum colour. The temporal evolution of this impact (i.e. COPD stability) is a dynamic term. “Stability” is a

longitudinal concept that requires the absence of exacerbations and deterioration in the aforementioned variables or in CAT or CCQ scores. Hence, control is defined as a condition that has both low impact (adjusted for severity) and stability (14).

Having proposed the concept of control in COPD, it is now important to establish whether it has clinical validity and utility, specifically in terms of predicting outcomes and guiding on-going COPD management (and/or whether the measure may benefit from further refinement).

## **1.2. Compliance statement**

This study will be conducted in full accordance with the International Conference on Harmonisation (ICH) Good Clinical Practice (GCP) Consolidated Guideline (E6) and any applicable national and local laws and regulations (e.g. European Union [EU] Directive 2001/20/EC and 2005/28/EC). Any episodes of noncompliance will be documented.

The investigators are responsible for performing the study in accordance with this protocol and the applicable GCP guidelines for collecting, recording, and reporting the data accurately and properly. Investigator Agreements to conduct and administer this study in accordance with the protocol will be documented in separate study agreements with the sponsor.

Each investigator is responsible for ensuring the privacy, health, and welfare of the patients during and after the study and must ensure that trained personnel are immediately available in the event of a medical emergency. Each investigator and the applicable study staff must be familiar with the background and requirements of the study.

The Chief Investigator has overall responsibility for the conduct and administration of the study at different study centres and the Principal Investigators in each local study centre have the overall responsibility for the conduct and administration in each individual local study centre.

